Subjects (approximately, to allow for withdrawals) will be recruited from clinics, trial registers and pulmonary rehabilitation (PR) waiting lists along with subjects identified from primary care COPD registers and poster response from displays at GP practices and hospitals. Subjects will be randomised to one of 3 groups (control:PR:LAMA) in a 1:2:2: allocation for phase 1 and a 1:1:4 for phase 2 of the trial. The aim will not be to evaluate the interventions but simply to produce a range of change in performance so that the changes in the exercise tests employed can be evaluated. The five most commonly reported exercise tests, strength testing and the Short Physical Performance Battery will be examined at baseline and after 6 weeks of the intervention or control period. The outcome measures will be conducted by blinded assessors. A planned analysis will be conducted after the 50th patient's last visit to confirm that commitment of the full resource and the 'opening' of other sites will deliver the desired data.

Eligible participants

The subjects will have a confirmed diagnosis of COPD and have GOLD stage 2-4 disease, and MRC grade dyspnoea2 or greater. Participants will be restricted to 40-85 years, so that they align with the 'classic' COPD patient. Since the aim is to compare different exercise outcomes, participants will not be stratified by exercise performance at baseline. However review of two sites (Leicester and RBHT) entrants to pulmonary rehabilitation programs suggests, based on ISWT data, that ~80% of participants will have an 6MWT <350m¹.

Exclusion criteria

Participants will be excluded from the trial if they have co-morbidities that limit the ability to walk/cycle, for example musculo-skeletal, arthritic, or neurological disorders. Common COPD co-morbidities such as controlled hypertension or heart failure will not be excluded, but will be documented. Since rehabilitation

¹ For example of 173 consecutive subjects in a currently submitted MS from Harefield the 75th centile for ISWT was 283m.

is one of the interventions, subjects who have participated in rehabilitation over the last 12 months will also be excluded, simply because they may not then gain additional benefit. Participants using LTOT therapy will also be excluded as will those requiring oxygen therapy during the course of an exercise test (i.e. desaturation documented below 85%)

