Subjects will perform a maximal symptom-limited incremental exercise test on an electrically-braked cycle ergometer (ramp protocol, increments 10Watts/minute) and an endurance cycle test conducted at 85% of peak workload. Ventilation and gas exchange measurements will be made throughout the exercise tests using a breath-by-breath computerised system³. Initial, end-exercise, 3 minutes recovery and during loaded testing (every 2 minutes), the Borg breathlessness Score, RPE Score will be recorded along with reason for termination.. The same variables will be collected pre and post intervention/control periods and iso-time data with respect to peak performance measures on the initial assessment will be reported on post intervention measurements. All inhalers will be withheld for 6 hours prior to measurements. Other medications will remain unchanged. The variables reported from these laboratory based tests will be those conventionally reported and will include peak workload (watts), peak oxygen uptake (ml/min/kg) and ventilation (l/min). For the endurance test, exercise time will be an additional important outcome (secs). Prior to, upon completion and 3 minutes into recovery of laboratory testing, measures of HR, percutaneous oxygen saturation and BP will be recorded. Patient's safety and termination of testing will be conducted in accordance with ATS/ACCP (23).

2. Field based

Prior to and upon completion of the field based tests, measures of breathlessness, perceived exertion (Borg scores), HR, BP, and percutaneous oxygen saturation will be recorded. In addition the reason for termination (leg fatigue, SOB or combination) will be reported.

² http://publications.nice.org.uk/chronic-obstructive-pulmonary-disease-cg101

³ Glenfield uses a Medisoft ergocard gas analyser and Expair Software.

- 6 MWT this will be conducted along a 30 or 50m corridor according to the ATS guidelines (24). Encouragement will be standardised and a practice walk completed. Conventionally the output from the 6MWT is expressed in metres. We will record the number and duration of any breaks in walking taken by the patient. A total of 3 tests will be required (1 at visit 1 and 2 at visit 2) in order to test repeatability following familiarisation, before intervention.

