For each exercise test conducted in the laboratory an online gas analysis system will be employed. This will not be possible for field based exercise tests. The following baseline variables will be collected for all tests, not necessarily all on every occasion but where appropriate documented at every visit.

- 1. Baseline spirometry (lung volumes and diffusing capacity of the lung for carbon monoxide (DLCO) to be done at entry only)
- 2. Height/weight (BMI)/leg length(ASIS to Medial Malleolus)
- 3. Fat free mass index by bio-electrical impedance⁶
- 4. Resting Heart rate
- 5. Resting fingertip oxygen Saturation
- 6. MRC dyspnoea score
- 7. Resting Borg breathlessness & RPE Scale

At the start and end of each exercise test, as well as all performance measures we will record-

- 1. Saturation
- 2. Heart rate
- 3. Blood pressure
- 4. Borg breathlessness & leg exertion
- 5. Reason for termination
- 6. For the 6MWT we will record the number and time of stops.

At baseline and after 6 weeks the exercise tests will be conducted over 4 visits following a day of familiarisation.

Visit 1 (1 day visit or split over 2 consecutive days) – Familiarisation

Consent and Eligibility confirmation

⁵ So as a secondary aim possibly generating insights into order effects

⁶ Glenfield use Bodystat[®] 1500.

Subjects will be given the opportunity to attend the initial consent and eligibility screening (including spirometry) prior to committing to a whole or half day of testing.

- 1. Informed consent secured
- 2. Spirometry (gas transfer and full lung function test)
- 3. Individuals will be randomised to one of three groups as described in figure 1.
- 4. Baseline questionnaires
- 5. Apply physical activity monitors
- 6. Isometric muscle strength (QMVC)
- 7. Exercise testing will be completed in random order. There will be a minimum of 30 minutes rest between each test, in addition two activity monitors will be given to the individual, to be worn for 14 days (24 hours a day). These will also be worn during exercise testing for visits 1, 2, 3, 4 and 5 to gauge intensity and energy expenditure.
 - Maximal cardiopulmonary cycle test & Endurance cycle test
 - 6 MWT (practice)
 - ISWT (practice) & ESWT (practice)
 - SPPB

Visit 2 (two weeks later, after activity monitor data collection period) - Baseline

Exercise tests will be presented in random order. There will be at least 30 minutes rest between each test.

- a. Maximal incremental cardiopulmonary cycle test

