- b. 6 MWT (performed twice with a 30 min rest in-between)
- c. ISWT (performed twice with a 30 min rest in-between)
- d. Strength testing (QMVC)

Visit 3 (next day)

Three exercise tests will be conducted in random order. There will be at least 30 minutes rest between each test.

- e. ESWT (85% peak performance)
- f. Cycle endurance test (85% peak performance)
- g. SPPB

Retesting after completion of the 6 week intervention (visits 4 and 5), will comprise the following measures presented in the same order as baseline (visits 2 and 3). These tests will be completed by a blinded assessor, blind to the intervention and previous results. Two activity monitors will be given, to be worn during visits 4 & 5 and for a further 7 days (24 hours a day).

- 1. ISWT
- 2. 6MWT
- 3. ESWT, at same level as baseline
- 4. Maximal incremental cycle test
- 5. Endurance cycle test, at same workload level and RPM as baseline
- 6. SPPB
- 7. Strength testing (QMVC)
- 8. Health Questionnaires

At the completion of the interventions a global rating scale of change will be reported for each exercise test. This will allow the description of the MID using anchor and distribution based methods. The global rating scale will identify two levels of change (a little improvement and a greater level of improvement). The scale employed will be one recently described by Pepin et al (37) describing the MCID for the ESWT.

Power calculation

In order to calculate a sample size a literature search was conducted using the search terms Tiotropium and six minute walk (and variants e.g. 6MWT) to identify studies giving an estimate of the likely benefit of the drug. Results found are shown in Table 1.

n	Blinded Assessor	Baseline 6MWT (mean (SD))	Tiotropium 6MWT (mean (SD))	Reference	notes
30	n	344 (105)	363 (98)	Fernandes 2010 (38)	Additional use of LABA
38	У	490 (67)	+6 (19)	Oga 2000 (12)	Additional use of Oxitropium
41	n	403 (20)	429 (17)	Fujimoto (39)	-
38	n	222 (5)	+13.5 (2)	Um(40)	-
44	У	415 (75)	429 (70)	Okudan(21)	Single dose (after 120 minutes)

Table 1: Properties of trials investigating Tiotropium with the 6MWT.

Based on these data [name] (Statistician to the Royal Brompton hospital Biomedical Research Unit) estimated the following sample sizes for achieving an increase in 25m in 6MW with 80% power and p=0.05.

Reference	Tio 6MWT (SD of Change From BL)	Estimated Sample size
Fernandes 2010	100 *	128
Oga 2000	19	7
Fujimoto	20 *	7
Um 2007	2	1
Okudan 2006	75 *	73

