For this study we considered, first, that it was important not to have a falsely low sample size and second that most of our subjects would be receiving a LABA. We therefore selected the figure generated by Fernandes paper, of 128 subjects per group but reduced the size of the whole group by 2:2:1 allocation giving a total sample size of 320. The calculation has been reviewed by statisticians from both GSK and Novartis who suggested an interim analysis because of the large range of potential values obtained.

Data entry will be managed by the Leicestershire CTU and held on a secure database. At a pre-agreed time the data will be released to the investigating team, this will be upon completion of the initial baseline measures to explore the stability of the measures and final data release upon completion of the intervention arms of the study. There will is a planned interim data analysis during the intervention phase, after the LV of patient #50. The analysis plan will be pre-defined as described below. There will be a pre-planned sub group analysis on participants with a baseline 6MWT test performance of less than 350m.

Pilot study.

Over the first twelve months a pilot (feasibility) study will be conducted at a single centre (Leicester). Sixty subjects will be recruited allowing for a drop out of 10 and analysis of 50 subjects completing the intervention period & attending all visits; subjects will be randomised and followed up after randomisation to either intervention. The procedure will be as outlined above.

The analysis of this pilot data will be supported by statisticians from Novartis. Preliminary data will be used to confirm the initial power calculations.

For the pilot study web based randomisation, data entry and monitoring will be managed by the Leicester Clinical Trials Unit. The database will be developed to support the multi-centre trial.

Sample Size re-estimation following Pilot Study & Interim Analysis

Upon collection and analysis of interim data, the ESWT was chosen as the exercise measure to recalculate sample size requirements for phase 2. This measure showed high repeatability at initial visits and sensitivity to change within treatment relative to a suggested MCID of 45-85 seconds*. Interim results for ESWT reported a change from baseline of 59 seconds (SD=163 seconds) for the LAMA arm.

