Table 4: One-sample t-test power to detect 60sec change from ba	seline
---	--------

N needed	SD = 130	SD = 140	SD = 160
Power =80%	39	45	58

Randomisation allocation recruitment at Glenfield hospital, Leicester, can be seen in Table 5 (April 2015 – September 2016).

Allocation and Ratio	Control	PR	LAMA
1.2.2 (actual)	16	32	32
1.1.4 (actual)	2	2	10
Current allocated totals	18	34	42
Number required for LAMA (ESWT response of 60±160 sec with 80% power and alpha of 5	-	-	78 recruited 58 completed
New allocation for recruiting n=78 in LAMA (1:0:4)	9	0	36
Total recruited to trial	27	34	78

Table 5: Randomisation allocation over	er time
--	---------

To ensure rigor is maintained a randomisation allocation of 1:0:4 would recruit a further 9 subjects to the control group and a further 36 into the LAMA group.

Analysis Plan

All exercise test data will be analysed on a per protocol basis. All data will be assessed for normality and analysed using appropriate parametric or non-parametric statistics. Significance will be set at p<0.05 and differences will be expressed as mean and standard deviations (SD) or 95% confidence intervals.

Data will be presented as mean (SD) or median (IQR). Comparison of values obtained within the treatment(s) and the control groups will be made using a paired t test or the Wilcoxon signed rank test. All tests will be 2 tailed. Additional analysis will be done to determine the sensitivity and specificity of the other measures to detect the change in MCID. Similarly the sensitivity and specificity of the failure to detect change in the placebo will also be determined.

Reproducibility study – The baseline data will examine the test-re test reproducibility of each of the tests employed, including measures of strength. The primary variable for each test will be the conventional measure of performance. Data will be compared in two ways, firstly the intra-class correlation (ICC) will be reported and secondly limits of agreement using Bland & Altman techniques (41). The Bland & Altman plot will allow us to check the data for stability across a range of performance.

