Sensitivity study - Comparison between the exercise test outcome measures will be made at two separate time points, baseline and 6 weeks. The primary measure for each test will be the variable that is most commonly reported e.g. distance /time/peak oxygen consumption. We will assume that an MCID of 25m is meaningful for 6MWT (15), and assess the ability of other tests to predict this change. Attention will be paid to both floor and ceiling effects.

Data accumulated from individuals offered rehabilitation upon completion of either the control or LAMA arm will be analysed after the main trial has been completed. This data will allow a repeat measures analysis comparing the relative effect of two interventions upon the exercise tests. This is a secondary planned analysis.

Opportunities for sub studies

a) MCID - This study would afford the opportunity to test this assumption and identify an MCID for the exercise tests employed in this study. We will report the MCID in one of two ways, we will employ an anchor based approach and report a statistically general distribution based approach. In addition by relating observed changes in exercise performance to the CRQ we will aim to generate a further MCID for the exercise tests, since it has recently been suggested that an MCID may differ depending on the context and nature of the intervention (37).

Practical Considerations & timescale to do (plus Gant chart)

Three sites should be adequate to recruit the required number of subjects. We estimate that it would take 36 months to complete this study, the pilot study will be conducted over the first year with a recruitment target of n=50. After this pilot phase recruitment will be extended to 3 sites.

Pilot study

Allow 3 months to gain necessary recruitment approval, advertise and recruit staff. To confirm whether MHRA approval required. Completion of ethics submission.

Months 1-3	Finalise ethics approval/set up database & randomisation system with Leicester & staff training as required.	
Month 3-24	Recruit 50 subjects to study – completion of baseline measures	
Month 24-30	Completion of data collection and preliminary analysis	
Month 24-30	Change ethics for multi-centre study	
Month 30-33	Recruitment in place for other sites (2/3)	

Study extension (planned recruitment – 180 participants – 90 per site). Recruitment will continue seamlessly at the Leicester site but allow for 21 months recruitment from the end of the pilot data).

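### The pre-planned 6MWT <350 m subgroup is selected on the walk that starts 6MWT change, so regression to the mean inflates mainly the 6MWT change in that subgroup

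*Protocol*

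**What the plan says.** The subgroup is fixed in one sentence of the Protocol's Power calculation section: "There will be a pre-planned sub group analysis on participants with a baseline 6MWT test performance of less than 350m".

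Four other places determine what that sentence means in practice:

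- The visit list under Testing procedure identifies the baseline: "Visit 2 (two weeks later, after activity monitor data collection period) - Baseline". The visit 1 walk is listed as practice. At visit 2 the test is "6 MWT (performed twice with a 30 min rest in-between". The Protocol does not say whether the first, second, best or mean of these two walks counts.
- The field-test section confirms three walks before the intervention: "A total of 3 tests will be required (1 at visit 1 and 2 at visit 2) in order to test repeatability".
- The Sensitivity study paragraph sets the time points: "Comparison between the exercise test outcome measures will be made at two separate time points, baseline and 6 weeks".
- The Analysis Plan sets the test: "Comparison of values obtained within the treatment(s) and the control groups will be made using a paired t test or the Wilcoxon signed rank test".

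Under Eligible participants, the Protocol expects that about "80% of participants will have an 6MWT <350m". The Sensitivity study paragraph takes 25 m as the 6MWT MCID and asks how well the other tests predict a change of that size.

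**The concern.** A measured 6MWT is the participant's usual performance plus visit-to-visit error. Those who fall below 350 m at visit 2 include more people who walked below their usual level that day than above it. At six weeks the error is drawn afresh, so their mean 6MWT rises even if nothing has changed.

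In a treatment comparison the randomised arms would share this rise and it would largely cancel. Here the stated aim is not to evaluate the interventions but to compare the tests, and the planned tests are within-group. Selecting on the baseline of one competing test gives that test an advantage. Two results in the subgroup could be affected: the apparent responsiveness of the 6MWT beside the other tests, and the classification of participants as having gained 25 m, which is the reference the other tests are asked to predict.

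**Working it through.** **The plan's own figure.** The Protocol gives no figure for the subgroup. Its original sample size does settle which SD to use. A one-sample two-sided t-test with a 25 m change, SD 100 m, 80% power and alpha 0.05 needs n = 128, as stated. The 100 m is therefore used as an SD of change, and the table heads it so. The regression formula needs the between-patient SD at baseline. For the same planning study Table 1 gives 344 (105) m, so the SD used here is 105 m.

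**Inputs.** Cut 350 m; SD 105 m; either 80% below the cut (Eligible participants) or mean 344 m (Table 1). The ICC is not given in the Protocol. It is assumed to be 0.80 to 0.95 and means the correlation between baseline and six-week walks without true change.

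**Formula.** With normal values, equal variance at both times and no true change, let c = (350 − mean)/SD. The expected rise is (1 − ICC) × SD × φ(c)/Φ(c).

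- 80% below: c = 0.84, which implies a mean of about 262 m. φ/Φ = 0.280/0.800 = 0.350. Rise = (1 − ICC) × 105 × 0.350 = (1 − ICC) × 36.7 m.
- Mean 344 m: c = 6/105 = 0.057, so 52% lie below. φ/Φ = 0.398/0.523 = 0.762. Rise = (1 − ICC) × 105 × 0.762 = (1 − ICC) × 80.0 m.

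| ICC (assumed) | 80% below 350 m | share of 25 m | mean 344 m | share of 25 m |
|---|---|---|---|---|
| 0.95 | 1.8 m | 7% | 4.0 m | 16% |
| 0.90 | 3.7 m | 15% | 8.0 m | 32% |
| 0.85 | 5.5 m | 22% | 12.0 m | 48% |
| 0.80 | 7.3 m | 29% | 16.0 m | 64% |

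A simulation with 1,000,000 draws agrees: 3.7 and 7.2 m (80% below), 7.9 and 15.9 m (mean 344 m), at ICC 0.90 and 0.80.

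**On a standardised scale.** At ICC 0.90 to 0.80 the spurious standardised response mean of the 6MWT is 0.08 to 0.11 (80% below) or 0.17 to 0.25 (mean 344 m).

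**Other tests.** If errors at visit 2 are independent between tests, the others do not regress. If same-day errors correlate 0.3 or 0.5, another test of equal reliability shows about 30% or 50% of the 6MWT's standardised rise.

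**After the change.** Selecting on a separate walk with independent error brings the simulated 6MWT rise to between −0.1 and +0.1 m in all four simulated scenarios.

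**The case against.** **Is it only the 6MWT?** A reader might infer that no other test is touched. The documents do not support that. The ISWT, the incremental cycle test and the strength test share visit 2 with the baseline 6MWT, and a shared bad day would make them regress as well. The ESWT, endurance cycle and SPPB follow the next day. The tilt towards the 6MWT is then smaller, but it remains.

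**Is it large?** On the Protocol's own expectation of about 80% below the cut, truncation is mild and the bias is a few metres. The larger range needs a mean near 344 m, which comes from one cited study of 30 patients and does not fit the 80% expectation. Averaging the two visit 2 walks would reduce the bias, though not its day-level part. One could also take the 100 m SD of change literally. With SDs of 105 and 98 m it implies a correlation of (105² + 98² − 100²)/(2 × 105 × 98) = 0.52 and a rise of 18 or 39 m. That entry is asterisked and may not be a measured SD of change, so those figures should not be relied on.

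**Is the consequence only inferred?** The Protocol does not list the comparisons to be made in the subgroup, and an SAP may do so. This stands as a limit on what can be said about the final ranking. It does not remove the flaw, because the selecting variable, the baseline visit and the within-group test are all fixed in the Protocol.

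**Does the control arm deal with it?** Control members below 350 m would show the same drift, and subtracting it would remove the bias in expectation. Table 5 gives 27 controls in total. If 80% are below the cut, about 22 remain before dropout. At ICC 0.90 the SD of change in the subgroup is about 46.5 m, so the standard error is about 46.5/√22 = 10 m, against a bias of 3.7 m. It is a check, not a correction.

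**Conclusion.** The point holds in a limited form. In the <350 m subgroup, the visit 2 6MWT both selects participants and starts their 6MWT change, and the stated within-group tests leave the regression to the mean in place. The inflation falls mainly on the 6MWT. It is about 2 to 7 m if some 80% are below the cut, and 4 to 16 m only if the mean is near 344 m, against an MCID of 25 m. These figures rest on a baseline SD of 105 m, normal values, equal variance at both times, a single baseline walk, and an assumed ICC of 0.95 to 0.80.

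The direction is against the stated hypothesis that the 6MWT is the least sensitive test: the subgroup would make it look more responsive than it is. A reader might infer that the ranking of tests is reversed, or that the trial's main comparison is compromised. Neither is shown. The whole-sample analysis and the ESWT-based sample size do not depend on this cut.

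**What to change.** Define subgroup membership from the visit 1 6MWT and compute 6MWT change from the visit 2 6MWT, stating which visit 2 walk, or their mean, is the baseline. Visit 1 also precedes the washout that only the LAMA arm undergoes, so membership would not depend on it. Report the control-arm change in the same subgroup beside the treated arms, noting its imprecision. If the visit 2 definition is kept, present it as a sensitivity analysis with the direction and likely size of the bias stated.

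The cost is one sentence; all the walks are already scheduled. There are three drawbacks:

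- Some participants change subgroup: about 7 to 14% at ICC 0.95 to 0.80 if 80% are below the cut (some 10 to 20 of 139). If the mean is near 344 m it is about 10% at ICC 0.95, 18% at 0.85 and 20% at 0.80.
- Visit 1 is a practice walk, so learning means that a somewhat different share falls below 350 m. This changes who is in the subgroup but does not bring the bias back.
- The bias is fully removed only if errors at visits 1 and 2 are independent. A bad spell lasting across both would leave part of it.

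Modelling change against the average of baseline and follow-up 6MWT is not a good substitute, because it conditions on a post-treatment value.

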
Based on the interim results, approximately 90 evaluable subjects in the LAMA arm are required to provide >80% power to detect a 50sec change from baseline, assuming a standard deviation of 160sec and a one-sample, two-sided t-test at a significance level of 0.05. To account for a potential 25% dropout rate in Phase 2, 120 subjects will be randomized to the LAMA treatment arm.

The table below shows the number of evaluable subjects needed from the LAMA arm in Phase II to detect a 50 second change from baseline at either 80% or 90% power, given different estimates of standard deviation.

Table of one sample t test power to acted sosse change from baseline					
N needed	SD = 130	SD = 140	SD = 150	SD = 160	SD = 170
Power =80%	56	64	73	83	93
Power =90%	73	85	97	110	124

 Table 3. One-sample t-test power to detect 50sec change from baseline

As changes from baseline are not expected in a control arm, and pulmonary rehabilitation has demonstrated effects in all exercise measures in the interim analysis, these arms will serve mainly to provide additional study sensitivity data. Thus, the randomization allocation will change from 2:2:1 to 4:1:1 to make sufficient within-group comparisons. 30 subjects will be randomized to receive pulmonary rehabilitation and 30 subjects will be randomized as controls in order to provide 22 additional evaluable subjects, plus 8 more to account for a potential 25% dropout rate, in each arm. In total, 180 subjects will be randomized to Phase 2.

2. Sample size re-estimation

WP4 Exercise outcome study

The revised power calculation is aligned with the actual data from the interim analysis. This new calculation is based on a mean change in the ESWT of 60±160 seconds (as per interim analysis) with 80% power and alpha of 5%. A total of 58 subjects are required in the LAMA group and allowing for 25% attrition, a total of 78 recruited subjects are required in the LAMA (table 4). As stated above there is no specific target allocation for placebo or PR in phase 2. We propose to maintain the control arm to provide a negative control to the LAMA arm and reduce the study bias, and allow us to maintain blinding.

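### The randomised control arm is kept as a negative control, but no stated analysis compares the change in LAMA or PR with the change in control, so non-treatment change counts as test responsiveness

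*Protocol*

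**What the plan says.** The Power calculation section of the protocol states that the analysis plan is pre-defined in the text that follows, so the Analysis Plan section is the trial's stated method. It reads: "Comparison of values obtained within the treatment(s) and the control groups will be made using a paired t test", with the Wilcoxon signed rank test as the alternative. It adds "All tests will be 2 tailed" and "All exercise test data will be analysed on a per protocol basis".

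The interim re-estimation section sizes the LAMA arm on a one-sample test of change from baseline and changes the allocation to serve within-group comparisons. Its premise for the third arm is "As changes from baseline are not expected in a control arm". The later section, 2. Sample size re-estimation, keeps that arm for a comparative reason: "We propose to maintain the control arm to provide a negative control to the LAMA arm", and to lessen bias. It sets no target number for it.

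The only stated use of the control data beyond its own paired test is this: "Similarly the sensitivity and specificity of the failure to detect change in the placebo will also be determined". The one comparative model, a secondary repeated-measures analysis, compares the two interventions and not control.

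**The concern.** A negative control removes bias from the LAMA change only if the two changes are compared. Tested against zero in its own arm, the LAMA or PR change contains the treatment effect plus anything else that moves between baseline and six weeks: residual learning, regression to the mean, and expectation in an open-label trial.

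That the trial does not aim to evaluate the interventions does not remove the problem. The hypothesis ranks the tests by sensitivity, and non-treatment change need not be equal across tests. Before the intervention, the 6MWT and ISWT are each performed three times (once at visit 1, twice at visit 2). The ESWT, endurance cycle and incremental cycle are each performed twice. A ranking built on uncorrected change could partly be a ranking of how much practice effect is left in each test. The results are meant to inform regulators on the choice of outcome.

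**Working it through.** **Inputs.** From 2. Sample size re-estimation and Table 4: ESWT change 60 s, SD 160 s, 80% power, two-sided alpha 5%, 58 evaluable LAMA patients, 25% attrition. From Table 5: 78 LAMA, 34 PR and 27 control patients recruited in total. From the interim re-estimation section: ESWT MCID 45–85 s. Evaluable controls: 27 × 0.75 = 20.25, about 20.

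**Step 1, the plan's own figure.** One-sample t-test with noncentrality δ√n/SD = 60 × √58/160 = 2.86 on 57 df: power 80.2%. The smallest n for 80% is 58, and 58/0.75 gives 78 recruited. The other Table 4 entries (39 and 45) and all of Table 3 also reproduce. The calculation is correct for what it describes, a within-arm change from zero.

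**Step 2, what drift alone does to that test.** Suppose there is no treatment effect and an assumed non-treatment drift d on the ESWT (n = 58, SD 160 s, noncentrality d√58/160):

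| Assumed drift | Chance LAMA test is significant |
|---|---|
| 0 s | 5% |
| 5 s | 5.6% |
| 10 s | 7.5% |
| 20 s | 15% |
| 30 s | 29% |

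The documents give no drift figure; these values are illustrative only.

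**Step 3, what the control arm's own test can show.** Paired t-test, n = 20, true change 60 s; half-width = t(0.975, 19) × SD/√20, with t = 2.093. No control SD is given, so a range is shown:

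| Control SD | Power for 60 s | 95% CI half-width |
|---|---|---|
| 160 s | 36% | ±75 s |
| 130 s | 50% | ±61 s |
| 100 s | 72% | ±47 s |
| 80 s | 89% | ±37 s |

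If control change is as variable as LAMA change, a control arm improving by the full 60 s would be non-significant about 64% of the time.

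**Step 4, what the missing contrast would deliver.** LAMA minus control, 58 v 20, SD 160 s in both arms:
- Standard error = 160 × √(1/58 + 1/20) = 41.5 s.
- Half-width = t(0.975, 76) × 41.5 = 1.992 × 41.5 = ±83 s.
- Noncentrality for 60 s = 60/41.5 = 1.45, power about 30%.

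The within-arm LAMA half-width is 2.002 × 160/√58 = ±42 s. If the control SD is 80 s, the standard error is √(160²/58 + 80²/20) = 27.6 s and the half-width is about ±55 s.

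**The case against.** Several points on the other side stand.

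- A reader might infer a rule that a non-significant control test means no change, or that significance in LAMA without significance in control shows an effect. The protocol states no such rule, and it allows differences to be given with 95% confidence intervals.
- Paired tests are not the only responsiveness analysis. The Sensitivity study assesses how well other tests predict a 25 m change in 6MWT, and global-rating, CRQ-anchored and distribution-based methods are planned. The specificity analysis in untreated patients can be read as a rate of false response. None of these, as stated, adjusts for control change.
- A reader might set 30% power against the stated 80% as a contradiction. It is not one: the 80% is labelled as one-sample change from baseline, and power for LAMA versus control is never claimed.
- A reader might conclude that unequal practice biases the ranking towards the hypothesis that the 6MWT is least sensitive. That is possible but not shown. Visit 1 familiarises patients with the exercise tests, the ESWT practice follows its source paper, the interim reported high ESWT repeatability, and the ISWT has as many attempts as the 6MWT. No learning curves are given.
- The control SD of 160 s is borrowed from the LAMA arm, so 36% is one end of a range.

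These points limit the claim. They do not supply the comparison with control.

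**Conclusion.** The point holds in this form: the stated analysis is within-arm, the control arm's declared role is comparative, and no analysis connects the two. Any non-treatment change after baseline is therefore counted as responsiveness. Its size and direction are unknown. At an assumed drift of 5 to 10 s the effect on the LAMA test is slight (about 6% to 7.5% significant instead of 5%); at 20 to 30 s it is material (15% to 29%).

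Failure to detect change in about 20 controls is weak evidence of stability when the control SD is near 160 s, and reasonable evidence against a 60 s drift only if the SD is nearer 80 s. These figures assume 25% attrition among controls and approximately normal change scores. The documents do not support the stronger claims that the ranking is in fact biased towards the hypothesis or that the sample size calculation is wrong.

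**What to change.** In the Analysis Plan:

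- For every test, report the difference in mean change, LAMA minus control and PR minus control, with 95% CI, beside the within-arm change.
- Report control-arm change with its 95% CI, in place of reliance on failure to detect change.
- Rank the tests on control-corrected change, for example a standardised response mean computed from the active-minus-control difference. Keep the paired tests as supportive.
- Use change scores. Randomisation is at visit 1 and baseline at visits 2 and 3, so baseline is a post-randomisation measure and, for prior LAMA users in the LAMA arm, follows washout.
- Compare PR only with controls randomised while PR was open (16 + 2 = 18 recruited in Table 5), leaving out the 1:0:4 period. Adjust at most simply for allocation period; with 2 controls in the 1:1:4 period, finer stratification is not workable.
- State that the 80% power is for within-arm LAMA change only and does not extend to LAMA versus control (about 30% for 60 s, 58 v 20, SD 160 s in both arms).

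No new data are needed. The cost is precision: about ±83 s instead of ±42 s at SD 160 s in both arms, or about ±55 s if the control SD is 80 s. The headline result also moves to a contrast the trial was not sized for, so it should be presented as an estimate with its interval and not as a powered test.
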